**-the distance between TADs and tooth root and maxillary sinus, and the distance between two tooth roots.**

**-the root resorption**

### 3.14Statistical analysis

Two doctors with more than 2 years of clinical CBCT image analysis experience performed image superimposition and measurement: everyone measured images once, with a 1-day interval, for a total of 3 measurements, and the average value was

taken. The linear deviation of the mini-implant tip and cap and the angular deviation of the long axis of the mini-implant in the bucco-palatal, mesio-distal and vertical directions were measured. The results were analysed by the SPSS statistical package version 19.0 (Chicago, USA). The Kruskal-Wallis H test of the multiple independent samples method was used to compare the three groups of mini-implant' deviation in the three directions. For the values that did not conform to a normal distribution, the Bonferroni method was used to correct the significance level for pairwise comparisons. One-way ANOVA was used for values that conformed to a normal distribution. P value less than 0.05 will be considered significant.

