#### **3.5.1 Objective 1**

Sample size calculation based on the objective 1 related to the of guide on the miniscrew implantation. In a previous study the response within each subject group was normally distributed with standard deviation 1.82437mm([name],Song Hui and Xiaofeng Huang,2022). If the true difference in the experimental and control means is 2.7403, the research will need to study 8 experimental subjects and 8 control subjects to be able to reject the null hypothesis that the population means of the experimental and control groups are equal with probability (power) 0.8. The Type I

error probability associated with this test of this null hypothesis is 0.05. The effective size is 1.5451013.

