#### **The angle deviation of the TADs.**

Miniscrew at BP		Miniscrew at MD		Miniscrew at VD	
Right side	left side	right side	left side	right side	left side

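### Section 3.14 applies independent-samples tests to mini-implant deviations, but the angle form has a right and a left value per participant and neither the screw count nor the unit of analysis is fixed

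*Protocol*

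**What the plan says.** On the tests, section 3.14 states: "The Kruskal-Wallis H test of the multiple independent samples method was used to compare the three groups of mini-implant' deviation". It adds "One-way ANOVA was used for values that conformed to a normal distribution" and "P value less than 0.05 will be considered significant". The only averaging it describes is over repeat readings of the images. It gives no rule for combining two screws from one person and names no paired or random-effects analysis.

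On the unit of randomisation, sections 3.6 and 3.10 allocate 24 participants, 12 per group. Sections 3.5.1 to 3.5.4 size the trial in subjects per group.

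On the data, Annexure A (section 4.1) is headed by a name and reference number, so one form belongs to one person. Its table "The angle deviation of the TADs" has a right-side and a left-side column under each of the three directions. The linear-deviation table in the same annexure has cap and tip columns and no side. The forms for safety (Annexure B) and stability (Annexure C) record no side either.

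On the number of screws, no figure is given. Sections 3.10 and 3.11 use both singular and plural wording, and section 3.12 describes one mini-implant.

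**The concern.** Angle deviation is one of the main efficacy indicators in section 3.13 and part of that section's definition of accuracy, which is the subject of objective 1. For this outcome the form has room for two values from one randomised person, while the test names the mini-implant as the thing compared and assumes independent observations.

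Two screws in the same mouth share the patient's anatomy and the same registration of CBCT to digital model, so their deviations are plausibly correlated. If both go into Kruskal-Wallis or ANOVA as separate observations, the test credits the trial with more information than 24 people supply. P values are then too small, and a difference in accuracy is declared by chance more often than the stated 5%.

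The protocol also leaves the number of observations open. With 24 participants an analyst could use 24 values, up to 24 × 2 = 48, or one chosen side. In a trial of 12 per group that choice could alter the accuracy conclusion.

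**Working it through.** **1. The plan's own figure, to establish its unit.** Section 3.5.1 sets the error rate ("error probability associated with this test of this null hypothesis is 0.05") and the power ("population means of the experimental and control groups are equal with probability (power) 0.8"). A two-sided two-sample t-test at 0.05 with power 0.80, using the effect sizes printed in section 3.5, gives:

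| Objective | Printed effect size | Computed n per group | Rounded | Protocol |
|---|---|---|---|---|
| 1 | 1.5451 | 7.67 | 8 | 8 |
| 3 | 1.3930 | 9.16 | 10 | 10 |
| 4 | 1.7990 | 5.98 | 6 | 6 |

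The largest is 10. Adding 20% gives 10 × 1.2 = 12 per group, or 24 in total, as stated. These counts are subjects with one value each. Whether the printed effect sizes follow from the printed differences and standard deviations is a separate question and does not affect this point.

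**2. Inputs for the error rate.**
- Nominal level 0.05, from section 3.14. Sidedness is not stated; two-sided is assumed.
- Two groups of 12 participants, from sections 3.6 and 3.10. Section 3.14 speaks of three groups; the two randomised groups are used here.
- Two screws per participant, both entered as separate observations: an assumption.
- Within-participant correlation (ICC): not given; assumed over the range 0 to 1.

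**3. Formula.** With m screws per participant, the variance of a group mean is multiplied by 1 + (m − 1) × ICC, which is 1 + ICC for m = 2. A test that ignores this understates the standard error by the factor √(1 + ICC), so the actual error rate is

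α = 2 × [1 − Φ(1.96 / √(1 + ICC))].

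For example, at ICC 0.5, 1.96 / √1.5 = 1.600 and α = 0.110.

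**4. Results.** The formula is set beside simulations of 20,000 trials per ICC, with normal data and 12 participants per group with two screws each.

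| Assumed ICC | Formula | Simulated t-test (two-group ANOVA) | Simulated Kruskal-Wallis |
|---|---|---|---|
| 0 | 0.050 | 0.048 | 0.047 |
| 0.1 | 0.062 | 0.062 | 0.058 |
| 0.3 | 0.086 | 0.087 | 0.082 |
| 0.5 | 0.110 | 0.114 | 0.107 |
| 0.7 | 0.133 | 0.133 | 0.127 |
| 0.9 | 0.155 | 0.165 | 0.155 |
| 1 (limit) | 0.166 | not run | not run |

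The formula reaches 0.10 when √(1 + ICC) = 1.960 / 1.645, that is, at ICC = 0.42.

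**5. After the fix.** With one mean per participant (12 against 12), the simulated error stays between 0.048 and 0.053 for both tests at every ICC tried from 0 to 0.9.

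**6. One screw each.** With m = 1 the multiplier is 1 + 0 × ICC = 1 and the error rate is 0.05 whatever the ICC.

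**The case against.** The strongest reply is that the protocol never says two screws are placed in each participant, nor that two sides enter as separate observations. Only the angle table records side. The linear table does not, and neither do the safety and stability forms. Several passages describe a single screw, and the plurals can refer to screws across participants. Side columns on a blank form would also suit one screw entered under whichever side was treated. In 3.14, the mini-implant may simply name the object measured, and independent samples may refer to the two randomised groups, which are independent. The only unit the protocol counts is the subject. Finally, how bilateral values are combined is often left to an analysis plan.

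Much of this stands. A reader might infer that every participant has two screws and that the type I error is about double its nominal level. The documents do not support that. Doubling needs both sides to be entered separately and a correlation of about 0.42, and the protocol gives neither. A shared guide cannot be cited as a source of correlation in both groups, because the control group has none.

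The reply does not remove the point. The protocol itself names the tests and the object compared, and its own form provides for two values per person on a main indicator. Nothing in it decides whether those values are one observation or two.

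**Conclusion.** The point holds conditionally. The protocol fixes tests that need independent observations, but not the number of screws per participant or the unit of analysis, and its angle form allows two values per randomised person. If both sides are treated and analysed as separate observations, the type I error lies between 0.05 and about 0.17: about 0.06, 0.09, 0.11 and 0.13 at assumed correlations of 0.1, 0.3, 0.5 and 0.7. This assumes two screws in every participant, a two-sided test and a correlation that is not negative. If only some participants have two screws, the inflation is smaller. With one screw each it is nil. The evidence for two values per person is confined to the angle deviations.

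**What to change.** State in the protocol how many screws each participant receives, and add to section 3.14 that the participant is the unit of analysis. Where right and left screws both exist, either average the two deviations per participant before the group test, or fit a mixed model with a participant random effect. Averaging leaves the named tests usable and is the simpler choice with 12 per group; the mixed model is useful if some participants have one screw and others two. If screws can be placed on both sides, record side in the linear-deviation table as well.

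The cost is a sentence or two and, at most, a side column on one form. No additional measurements are needed, the sample size stays at 24 because it already counts subjects, and the wording does no harm if every participant turns out to have one screw.

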#### **Randomization:**

**In this study, participants will be randomly assigned to either the Intervention group or the control group using a computerized random number generator.**

We will use simple randomization. Assuming 24 participants, we randomly assigned them to two groups (trial and control) of 12 participants each. The steps are as follows: generate 24 random numbers using a random number generator. Sort these random numbers. The first 12 were assigned to the intervention group and the last 12 to the control group. Ensure that participants are assigned to the corresponding group in this order.

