## 3.10 Data collection and grouping

Twenty four (24) individuals who met the criteria will be randomly divided into 2 groups, 12 will be selected as the experimental group and mini-implants will be

implanted using guide plates, while others 12 participants will be selected as the control group and implanted mini-implants based on experience and no guide plates.

**The recruitment will take about two months, using hospital bulletin boards and social media at Beijing Xuanwu TCM Hospital. All routine orthodontic diagnostic records will be collected. The patient was asked to sign an informed consent form before surgery, which took about 20 to 30 minutes. The doctor implanted the miniscrew, and the operation time was about half an hour. The study design will be used as assigning intervention and control group randomly. The postoperative clinical and imaging evaluation was about 6 months.**

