### 3.13 Analyses and measurements:

#### 1. Main efficacy indicators.

A. CBCT analysis indicators: Based on the ideal position of the implant designed before surgery as the standard, the researcher will measure the linear deviation of the tip and cap of the TADs in the mesio-distal, buccal-lingual, and vertical three-dimensional directions, the angle deviation of the tip and cap of the TADs in the mesio-distal, buccal-lingual, and vertical three-dimensional directions, the distance between TADs and tooth root and maxillary sinus, and the distance between two tooth roots.

B. Clinical data analysis: The mobility of TADs. : The stability of a miniscrew can be evaluated through clinical examination by checking for mobility, and implant loosening and displacement.

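### Section 3.14 sets out a three-group analysis for a two-arm trial, and none of at least nine deviations tested at 0.05 is named as the one that decides accuracy

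*Protocol*

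**What the plan says.** The design has two arms. The randomisation text in section 3.6 says "we randomly assigned them to two groups (trial and control) of 12 participants each", and section 3.10 repeats it: "Twenty four (24) individuals who met the criteria will be randomly divided into 2 groups". Sections 3.5.1 to 3.5.4 size every objective as experimental against control, and hypothesis 1 in section 1.11.4 contrasts screws placed with and without the guide.

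The analysis in section 3.14 is written for a different design. The Kruskal-Wallis test "was used to compare the three groups of mini-implant' deviation in the three directions". For values that are not normally distributed, "the Bonferroni method was used to correct the significance level for pairwise comparisons". Normally distributed values go to one-way ANOVA. The only threshold is: "P value less than 0.05 will be considered significant".

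The measures in section 3.14 are "The linear deviation of the mini-implant tip and cap and the angular deviation of the long axis of the mini-implant", each in the bucco-palatal, mesio-distal and vertical directions. Section 3.13 puts the deviations, together with distances and screw mobility, under the heading "Main efficacy indicators". It describes the angle differently, as "the angle deviation of the tip and cap of the TADs". Section 3.5.1 gives a standard deviation of 1.82437 mm and a difference of 2.7403 for objective 1, without saying whether they refer to tip or cap, or to which direction.

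**The concern.** An analysis text that counts three groups cannot be carried out as written on two arms. The more serious consequence is for control of the false-positive rate. The one adjustment in the protocol acts on pairs of groups, and with two arms there is a single pair. The multiplicity that does exist lies in the number of deviations compared, and the stated text does nothing about that.

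Hypothesis 1 speaks of a significant difference in accuracy without saying which deviation settles it. A claim of better accuracy could therefore rest on whichever deviation reaches 0.05. For the same reason, the objective 1 power statement cannot be tied to any named result.

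**Working it through.** **1. Groups and pairs.** With k groups there are k(k-1)/2 pairs. For k = 2 that is 1, so the Bonferroni threshold is 0.05/1 = 0.05, which is no correction.

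**2. Do the named tests still work with two groups?** Yes. In a numerical check on two samples of 12, one-way ANOVA gave the same p-value as the two-sample t-test. Kruskal-Wallis gave the same p-value as the rank-sum test (normal approximation, no continuity correction).

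**3. Could the three groups be the three directions?** No. The directions are measured on the same screw, so they are not independent samples as the test requires. Comparing directions would also not compare guide with no guide.

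**4. Number of measures in section 3.14.** Linear: 2 sites (tip, cap) x 3 directions = 6. Angular: 1 long axis x 3 directions = 3. Total: 9. Distances and mobility, also main indicators in section 3.13, come on top of this.

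**5. Chance of at least one false positive, all nine nulls true, 0.05 each.**
- Independent measures: 1 - 0.95^9 = 0.370.
- Correlated measures (simulation, t-tests, 12 per arm, equal pairwise correlation): 0.326 at 0.3, 0.278 at 0.5 and 0.211 at 0.7. With 10 per arm the values are 0.332, 0.275 and 0.212.

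The protocol gives no correlations, so this range is an assumption.

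**6. The plan's own sample size for objective 1.** Inputs from section 3.5.1: difference 2.7403, SD 1.82437, alpha 0.05, power 0.8, stated effect size 1.5451013. Two-sided testing is assumed because hypothesis 1 has no direction.
- Stated effect size 1.5451: n = 7.67, so 8 per arm, as the protocol says (power 0.819).
- From the inputs, d = 2.7403/1.82437 = 1.502: n = 8.04, and power at 8 per arm is 0.798.

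The stated 8 per arm is reproduced for one two-group test of one measure at 0.05. Nothing in it allows for nine tests.

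**7. Power at the planned size** (two-sample t-test, noncentral t; 12 per arm as randomised, 10 per arm as the largest requirement before the 20% dropout allowance):

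| Rule | Alpha | 12 per arm, d = 1.502 / 1.545 | 10 per arm, d = 1.502 / 1.545 |
|---|---|---|---|
| One named primary | 0.05 | 0.940 / 0.951 | 0.888 / 0.904 |
| Bonferroni over 9 co-equal measures | 0.05/9 = 0.00556 | 0.720 / 0.751 | 0.590 / 0.623 |

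The second row is the power for any one measure that has this effect. The effect is in mm, so it can apply only to a linear deviation and not to the angles.

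**The case against.** The best defence is that the three-group wording does no harm to any single result. On two groups the software returns the two-sample answer, and each p-value is valid for its own measure. That stands. A reader might infer from the mismatch that the tests are invalid; they are not.

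It can also be said that a multiplicity rule across outcomes commonly belongs in a statistical analysis plan, which is not at hand. That stands as far as a mere omission goes. But the protocol here fixes the number of groups, the tests, the correction and the threshold, and lists all the deviations as main indicators. A later plan would have to contradict that text to put it right.

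Three stronger readings are tempting but not supported:
- **Twelve measures instead of nine.** Section 3.13 mentions the angle at tip and cap, and Annexure A has six angle columns. Those columns are right and left side, not two ends of the screw. A rigid screw has one long axis, so the section 3.13 wording may simply be a loose description of the section 3.14 angle.
- **A stricter three-pair threshold applied to everything.** Section 3.14 limits the Bonferroni step to non-normal values, and two arms supply only one pair.
- **A significant deviation would mean nothing.** The percentages above are the chance of any false positive when every null is true. They do not measure the evidence in a particular observed result.

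**Conclusion.** The analysis text is wrong as written. It describes three groups where the design has two, and its only correction is empty for this trial. No measure is fixed to decide hypothesis 1.

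If any one significant deviation out of nine is taken to show a difference in accuracy, the false-positive chance is 37% under independence and roughly 21% to 33% at correlations from 0.7 down to 0.3, against a stated 5%. This rests on the count of nine, on the assumed correlations, and on the any-one-counts reading, which the protocol neither adopts nor rules out.

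The planned 24 patients are enough for objective 1 on its own assumptions, provided one linear deviation is primary and the objective 1 effect applies to it. If all nine stay co-equal and are corrected by Bonferroni, power for any one of them falls below the planned 80%.

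**What to change.** 1. In section 3.14, delete the three-group and pairwise Bonferroni text. Compare the two arms by t-test or rank-sum test with a 95% confidence interval, using one value per patient. If patients have screws on both sides, as the right and left columns in Annexure A suggest, average the sides or use a model that accounts for clustering within patient. If the matching described in section 3.6 is kept, use a paired analysis instead.
2. In sections 3.5.1 and 3.13, name one primary linear deviation (tip or cap, and direction), namely the one to which the objective 1 standard deviation and difference refer. Make all other deviations secondary.
3. Use one definition of the angle throughout. Section 3.14 takes the long axis, sections 3.9.2.3 and 3.13 refer to two ends of the screw, and Annexure A splits by side.

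The cost is wording in sections 3.5.1, 3.9.2.3, 3.13, 3.14 and Annexure A, with no new data and no more patients. The primary must be chosen before any outcome data are seen. The downside is that fewer results can be called confirmatory.

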### **3.7.3 withdrawal criteria**

**(1)Patient's miniscrew implantation position develops an infection**

**(2)Patient who produces persistent pain or discomfort that cannot be managed**

**(3)Significant bone resorption around the miniscrew site**

**(4.)The miniscrew becomes loose or shifts position,**

[figure not shown]

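### Section 3.14 picks ANOVA or Kruskal-Wallis by a normality check and names no unequal-variance test, so type I error can exceed 5% if both spread and losses differ by arm

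*Protocol*

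**What the plan says.** Section 3.14 covers the linear deviation of tip and cap and the angular deviation of the long axis, each in three directions. That makes 2 × 3 + 3 = 9 deviations, all among the main efficacy indicators of Section 3.13. The rules are:

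- The rank test comes first: "The Kruskal-Wallis H test of the multiple independent samples method was used to compare the three groups of mini-implant' deviation in the three directions".
- A Bonferroni correction of pairwise comparisons is then tied to whatever fails the normality check.
- Whatever passes the check is handled differently: "One-way ANOVA was used for values that conformed to a normal distribution".
- The significance threshold is set at 0.05.

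I read these together as a switch applied to each deviation: ANOVA if it looks normal, Kruskal-Wallis with Bonferroni otherwise. No normality test or threshold is given. The reference to three groups does not match the two-arm design of Sections 3.6 and 3.10.

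On spread, Section 3.5.1 plans with one figure: "the response within each subject group was normally distributed with standard deviation 1.82437mm". On losses, Section 3.5 allows 20% overall with no split by arm. Section 3.7.3 lists as a reason for withdrawal: "The miniscrew becomes loose or shifts position".

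**The concern.** One-way ANOVA on two arms is the equal-variance t-test. If the variances differ, its error rate depends on which arm is smaller: it is too high when the more variable arm is the smaller one, and too low in the reverse case. Kruskal-Wallis tests location only when the two distributions have the same shape and spread.

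The trial's rationale makes unequal spread plausible. Section 1.10 presents freehand insertion as error-prone and the template as a standardising tool. Withdrawal for loose or shifted screws could also fall more on controls if the guide works. If both happened, the main accuracy comparisons would reject a true null more often than the stated 5%.

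Separately, a normality check on about 12 values per arm may send tip to a comparison of means and cap to a comparison of ranks for no substantive reason.

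**Working it through.** **1. The plan's own figure.** Section 3.5.1: "If the true difference in the experimental and control means is 2.7403, the research will need to study 8 experimental subjects and 8 control subjects"; "The effective size is 1.5451013". The printed inputs give 2.7403 / 1.82437 = 1.502, with power 0.798 at 8 per arm. The printed effect size 1.5451 gives power 0.819 at 8 per arm. The figure therefore reproduces as a two-sample t-test with one SD. The final size follows from objective 3: 10 × 1.2 = 12 per arm, 24 in all.

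One hint of two SDs can be tested. The printed effect size implies an SD of 2.7403 / 1.5451013 = 1.7735. If that is the root mean square of two arm SDs, one of them 1.82437, the other is √(2 × 1.7735² − 1.82437²) = 1.721. The ratio is then 1.06. This is an inference, and it gives no support for a large ratio.

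**2. Why arm sizes matter.** Set the guide SD to 1 and the control SD to 2. ANOVA takes the variance of the mean difference as s²(1/n_g + 1/n_c), where s² on average is [(n_g − 1)·1 + (n_c − 1)·4] / (n_g + n_c − 2). The true variance is 1/n_g + 4/n_c.

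- 12:12: s² = 2.5; assumed 2.5 × (1/12 + 1/12) = 0.417; true 1/12 + 4/12 = 0.417. They agree.
- Guide 12, control 8: s² = (11 + 28)/18 = 2.167; assumed 2.167 × 0.2083 = 0.451; true 1/12 + 4/8 = 0.583. The standard error is too small by a factor √(0.451/0.583) = 0.88.
- Guide 8, control 12: s² = (7 + 44)/18 = 2.833; assumed 0.590; true 1/8 + 4/12 = 0.458. The standard error is too large by a factor 1.13.

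**3. Error rate of the rule as written.** The following are assumed, because the protocol does not give them: the SD ratios, the splits, two-sided 5% tests, Shapiro-Wilk at 0.05 in each arm as the normality check, and signed deviations with equal means. There were 20,000 simulated trials per cell, with a simulation standard error of about 0.2 points. Type I error (%) with normal data:

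| Guide : control analysed | SD ratio 1 | 1.5 | 2 | 3 |
|---|---|---|---|---|
| 12 : 12 | 5.0 | 5.6 | 5.9 | 6.3 |
| 10 : 10 | 5.3 | 5.3 | 5.5 | 6.5 |
| 12 : 10 | 5.3 | 6.3 | 7.1 | 8.4 |
| 12 : 8 | 5.1 | 7.3 | 8.7 | 11.2 |
| 12 : 6 | 5.2 | 8.9 | 11.8 | 15.6 |
| 8 : 12 | 5.1 | 3.9 | 3.4 | 3.3 |
| Welch, 12 : 8 | 4.8 | 5.0 | 5.1 | 5.2 |

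If 20% is lost evenly, 12 × 0.8 = 9.6, so 10:10 is the row closest to the plan. The 12:8 row loses 4 of 24, about 17% overall, all of it from controls. At the ratio of 1.06 from step 1, 12:8 gives 5.2%.

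**4. What the switch contributes.** At 12:8 and ratios 1.5 / 2 / 3, ANOVA alone gives 7.2% / 8.6% / 10.8%. The rule gives 7.3% / 8.7% / 11.2%, so the check adds 0.1 to 0.4 points. Its other effect is on consistency. With truly normal data at 12:12 it passes 90.5% of the time, so about 9 × 0.095 = 0.9 of the nine deviations would go to ranks by chance. With skewed data (gamma, shape 2) it passes about half the time.

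**5. Skewed data.** At 12:8 and ratios 1.5 / 2 / 3 the rule gives 8.5% / 11.6% / 14.8%, and Welch 6.1% / 7.1% / 8.0%. At 12:12 and ratio 2 the rule gives 9.3%.

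**The case against.** A reader might infer that error rates in this trial do exceed 5% and that its p values are too small. The documents do not support that.

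- **Spread.** No section gives an SD by arm or says that the guide reduces variability. Section 3.5.1 plans with one SD.
- **Losses.** No section says that controls will be lost more often. If guide patients are lost instead, the rule is conservative.
- **Timing.** Loosening follows insertion, so placement deviations measured at once need not be lost. This stands in part. Section 3.11 ties the immediate and 6-month time points to model scans, whereas accuracy is measured on CBCT. The time of the postoperative CBCT is not fixed, and Section 3.10 speaks of about 6 months of imaging evaluation.
- **Outcome scale.** The protocol does not say whether deviations are signed. If they are magnitudes, tighter placement around the plan is itself a smaller mean, so rejection would be a true finding.
- **Cause.** Removing the normality check alone would barely change the error rate. The change of test does the work.
- **SAP.** An unequal-variance option could stand in a SAP that is not shown. But Section 3.14 itself fixes a data-driven choice of test, and that is open to comment.

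All of this limits the size of the point. None of it supplies a reason for the switch.

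**Conclusion.** The concern holds in conditional form and is minor. Section 3.14 chooses the test from the data and names none that allows unequal variances. The error rate exceeds 5% materially only if control spread is larger, controls are the smaller arm, and deviations are signed: with normal data, about 7% to 11% at 12:8 for SD ratios 1.5 to 3. With equal arms and normal data the excess is at most about 1.5 points over the ratios examined. With equal SDs there is essentially none. Skewed data raise the figures, including at equal arm sizes. The ratios and splits are assumptions, and the protocol offers no figure to choose among them. Apart from error rates, the switch can leave tip, cap and directional results on different scales, which makes them hard to read together.

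**What to change.** In Section 3.14, in the same edit that corrects three groups to two, replace the normality-based choice with one rule: every accuracy deviation is compared between the two arms by Welch's test, reported with the mean difference and 95% confidence interval, and one rank test is given as sensitivity analysis. State also whether deviations are analysed as signed values or magnitudes.

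The cost is about a sentence or two and roughly a point of power at most. With equal SDs and the objective 3 effect size of 1.3930 (40,000 simulated trials), the rule as written and Welch have power 90.1% and 90.0% at 12:12, and 82.0% and 80.9% at 12:8. Welch only partly corrects strongly skewed data (about 6% to 8% at 12:8). If strong skew is expected, a studentized permutation test is an alternative to pre-specify.
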